7.4. Secondary analyses

7.4.1 Adjusting for "time to assessment clinic"

The primary analysis will be repeated including a variable which adjusts for the time between randomisation and assessment clinic. This variable will be included as a covariate in the model. The results for this can be found in **Table 15**.

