3.7. Sample size and justification

We estimate that 20% of patients who have had primary total knee replacement will have long-term post-surgical pain. Based on our recent trial in total knee replacement (Wylde V, 2015), we estimate conservatively that we will achieve a recruitment rate of 40% (an 8% conversion rate for number randomised out of those screened). Surgical audit data show that the four trial centres conduct over 1,900 primary total knee replacement procedures annually. Over 30 months, this equates to 4,750 procedures, and we estimate that 950 of these patients will have long-term post-surgical pain. With a recruitment rate of 40% we can recruit 380 patients over this period. In our recent trial we achieved 83% follow-up (Wylde et al, 2015); therefore, allowing for a generous 25% loss to follow-up in the STAR trial, a total of 380 participants randomised would yield 285 for analysis. For a 2:1 intervention:control randomisation ratio we would have a power of 80% to 90% to detect standardised differences of between 0.35 to 0.40 standard deviations (SDs) using a 2-sided 5% significance level. From previous studies (Dworkin RH, 2008), (Bruce J, 2014), the SDs for each of the BPI Interference and Pain Severity scales for patients with long-term postsurgical pain has been observed to be approximately 2, in which case the target effect size translates to a difference between intervention and control groups of between 0.7 and 0.8 scale points for both scales. Such a difference would be worthwhile detecting clinically, since the current consensus statement indicates that differences of approximately one scale point can be deemed the minimally important difference for both of these scales (Bruce J, 2014),(Kroenke K, 2009).

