4. GENERAL ANALYSIS CONSIDERATIONS

4.1. Analysis populations

The primary analysis of the data will be on a complete case basis, in accordance as far as possible with the intention to treat (ITT) principle whereby we analyse as randomised, disregarding protocol deviations or non-compliance. Sensitivity analyses will utilise imputation methods to handle missing data to ascertain whether their exclusion in the primary analysis has had any effect within an ITT paradigm. In addition, a crude per protocol analysis will be performed using those patients who adhered with the intervention sufficiently. Adherence to the intervention, for a patient in the intervention arm, is defined as the patient attending their assessment clinic appointment and for patients in the control arm, adherence cannot be measured as they adhere by using usual care. We assume that all patients in the control arm have adhered to the intervention allocation. This per protocol analysis will address the same points as the comparison based on groups as allocated (hereafter referred to as 'the ITT analysis') just using a different population. Since these results are likely to be biased, we will also use the Complier Average Causal Effect (CACE) approach to adjust for any selection effects in terms of adherence.

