7.3. Primary analysis

The primary and main secondary analyses will be conducted using the ITT principle (that is, comparisons of groups as allocated) using the appropriate regression model. Assumptions for each regression will be checked to make sure the correct method of analysis is being used.

Each of the co-primary outcome measures, BPI Severity and BPI Interference scales, will be analysed to compare treatment groups using linear regression. The models will be adjusted for trial centre as a fixed effect and baseline BPI pain scores. Estimates will be calculated of the effect that intervention has on each of the BPI scores compared with usual care. Primary analysis will be adjusted for variables which are imbalanced at baseline to see if this makes a marked difference to the unadjusted primary analysis.

Results from the primary analysis will be presented in **Table 14**.

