7.6.2 Per protocol and CACE analysis

We propose to carry out per protocol analyses. It will only compare individuals who remained in their allocated treatment group throughout the trial. Since this analysis is likely to be biased, we will also use the Complier Average Causal Effect (CACE) approach if the quantity of compliant patients (those patients in the intervention group who attend their initial assessment clinic and those in the control arm who continue with usual care) satisfies the rule which we state in section *6.4. Compliance.* This provides an unbiased estimate for the treatment effect for those who have complied with the treatment group allocation. Compliers would be defined as a patient who attends the assessment clinic (intervention). This approach would be justified if the characteristics of those who adhered to the comparator treatment differed from those that adhered to the intervention. Results from these analyses will be presented as in **Table 32** - **Table 44**. If there is differential adherence in the two arms we will also investigate structural mean approaches as described by Fischer et al (Fischer, Goetghebeur, Vrijens, & White, 2011) and, separately, use extensions of CACE as described by White et al (White, Kalaitzaki, & Thompson, 2011).

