9.5. Secondary outcomes results

Table 15: Secondary analysis – adjusting for 'time to assessment clinic'

	Usual	care		Intervention					
	N	Mean	SD	Ν	Mean	SD	Difference	95% CI	P-value
							in means ¹		
BPI Severity									
BPI									
Interference									

¹ Adjusted for trial centre and baseline OKS and 'time to assessment clinic'

Table 16: Secondary outcomes tables

	Usual care		Interve	Intervention		Difference in	95% CI	P-value	
		1				means		-	
	Ν	Mean	SD	Ν	Mean	SD			
BPI Severity									
BPI Interference									
OKS									
DN-4									
PainDETECT									
Pain Catastrophizing scale									
PaSol: Solving Pain									
PaSol: Meaningful life									
PaSol: Acceptance of pain									
PaSol: Belief in solution									
Patient Satisfaction									
ICECAP-A									
Short form-12									
HADS: Anxiety									
HADS: Depression									
Section A: Question 5									
Section D: Question 8									
Section L: Question 5									
				N	Odds ratio ¹	95% Cl	P-value		
Body Map (CWP(M))]	

¹ Adjusted for trial centre and baseline OKS

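### Time to assessment clinic is adjusted for in a two-arm model although it arises after randomisation and has no value for controls, so Table 15 is undefined, shifted or uninformative depending on an unstated coding

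*SAP*

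**What the plan says.** The primary model in section 7.3 is a linear regression of each BPI score on arm: "The models will be adjusted for trial centre as a fixed effect and baseline BPI pain scores". Section 7.4.1 then states: "The primary analysis will be repeated including a variable which adjusts for the time between randomisation and assessment clinic". On how the variable enters the model it says only: "This variable will be included as a covariate in the model". Table 15 in section 9.5 has the same layout as Table 14, with N, mean and SD per arm and then a difference in means, 95% CI and p-value. Its footnote reads "Adjusted for trial centre and baseline OKS and 'time to assessment clinic".

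Elsewhere the clinic is an intervention-arm event. Section 7.6.2 describes compliers as "those patients in the intervention group who attend their initial assessment clinic and those in the control arm who continue with usual care". Section 6.4 defines compliance in the same way, and Table 46 counts attendance only among those randomised to intervention. Section 4.1 is consistent with this, saying of the control arm that "adherence cannot be measured as they adhere by using usual care".

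No section gives a value, coding or centring of clinic time for controls or for intervention participants who never attend. The Stata code in the appendix covers questionnaire scores only. The amendment log (Table 51) shows that analysis of clinic timing was added on purpose in V2.2.

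**The concern.** A covariate in a two-arm regression needs a value in both arms and should not be a consequence of allocation. Time to clinic fails on both counts: it starts at randomisation, and one arm has no clinic. The SAP therefore names a model whose arm coefficient has no fixed meaning until someone chooses what to enter for controls, and that choice determines the answer.

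Two cells of Table 15 are at stake, the adjusted differences for BPI Severity and BPI Interference. Because the layout matches Table 14, a reader will set the two side by side. A larger difference in Table 15 could be taken as evidence that delay diluted the effect, and a similar one as reassurance. Neither reading would be sound. Section 1 also gives as a purpose that another analyst could carry out the work from the document; here two analysts could report quite different results from the same data.

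**Working it through.** **Inputs from the SAP (section 3.7).** 380 randomised, 25% loss, 2:1 allocation, SD about 2, target difference 0.7 to 0.8 points, "using a 2-sided 5% significance level".

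- Analysed: 380 × 0.75 = 285, that is 190 intervention and 95 control.
- SE of the arm difference: 2 × √(1/95 + 1/190) = 0.251.
- Power by normal approximation: Φ(0.7/0.251 − 1.96) = 79.5% and Φ(0.8/0.251 − 1.96) = 88.9%. The stated 80% to 90% is reproduced and is not in dispute.

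**Assumptions, not in the SAP.** All 190 intervention participants have a wait. The ratio r of mean wait to SD of wait is 1 to 3. For the simulation (2,000 runs per setting, without centre or baseline BPI), the wait has mean 4 and SD 2 in arbitrary units. The effect of waiting is 0 to 0.2 BPI points per unit. The wait correlates 0 or 0.3 with a prognostic factor that correlates 0.5 with outcome.

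**Coding A: controls left missing.** Section 4.1 makes the primary analysis complete-case, so repeating it with this covariate removes every control. Arm is then constant. The design matrix of intercept, arm and time has rank 2 of 3, and the arm coefficient cannot be estimated. Intervention non-attenders are lost as well.

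**Coding B: controls set to 0.** The model is Y = a + bZ + cZW, with Z the arm and W the wait. The estimate of b is D − c × (mean wait), where D is the ordinary arm difference: the effect projected back to a wait of zero. Its variance is

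s²[1/95 + 1/190 + r²/190], against s²[1/95 + 1/190] without W.

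Since 1/95 + 1/190 = 3/190, the SE ratio is √(1 + r²/3):

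| r (assumed) | SE ratio | increase |
|---|---|---|
| 1 | 1.15 | 15% |
| 1.5 | 1.32 | 32% |
| 2 | 1.53 | 53% |
| 3 | 2.00 | 100% |

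The simulation has r = 2. With no wait effect and no confounding, the empirical SE rose from 0.25 to 0.39 and power at D = −0.7 fell from 0.81 to 0.44.

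The shift follows from c. Confounding of 0.3 adds 2 × 0.5 × 0.3/2 = 0.15 to c, so the expected estimate is D − 4c:

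| wait effect per unit | correlation | c | expected, D = −0.7 | simulated, D = −0.7 | simulated, D = 0 | rejection, D = 0 |
|---|---|---|---|---|---|---|
| 0 | 0 | 0 | −0.70 | −0.703 | 0.007 | 5.2% |
| 0 | 0.3 | 0.15 | −1.30 | −1.315 | −0.611 | 36.0% |
| 0.1 | 0 | 0.10 | −1.10 | −1.095 | −0.408 | 17.2% |
| 0.1 | 0.3 | 0.25 | −1.70 | −1.719 | −1.031 | 75.4% |
| 0.2 | 0 | 0.20 | −1.50 | −1.502 | −0.799 | 52.6% |
| 0.2 | 0.3 | 0.35 | −2.10 | −2.134 | −1.412 | 95.6% |

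The second row is the clearest case of bias: waiting has no effect, the intervention has none, and the test still rejects 36% of the time. In the rows with a wait effect and no confounding, the estimate is right for a wait of zero, but it answers a different question from Table 14.

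**Coding C: time centred at the intervention-arm mean, controls set to 0.** The covariate averages zero in both arms, so the arm coefficient equals D. In every setting the simulated mean matched the estimate without the covariate (−0.70 to −0.71 at D = −0.7). With centre and baseline BPI in the model the equality is approximate, but the conclusion is the same: the adjustment adds nothing to the arm comparison.

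**The case against.** A reader might infer that no version of this analysis can give a valid between-arm effect. The SAP does not support that. Coding C gives a valid one; it simply repeats the comparison without the covariate. The accurate statement is that the coding is unspecified and the result depends on it.

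A reader might also infer that all controls are certain to be dropped. The SAP contains no code for this variable, so that happens only if controls are left missing.

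The sizes under coding B rest on an assumed wait distribution. The SAP gives no mean or SD of waiting time, and non-attenders would reduce the 190. That waiting time is related to prognosis is plausible but not documented. These points limit the figures. They do not touch the loss of estimability under A or the changed target under B, which follow from the form of the model.

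Finally, this is one supplementary repeat among the secondary analyses. No decision rule uses Table 15, and the SAP does not call it a robustness check on Table 14. That stands, and it sets the priority. What remains is that the plan promises a between-arm estimate with a p-value for both co-primary outcomes from a model that does not define it.

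**Conclusion.** The point holds for section 7.4.1 and Table 15. The covariate is post-randomisation by its own definition and exists only for intervention participants who attend. Of the three natural codings, one cannot be fitted as a two-arm comparison, one moves the target to zero wait and is open to confounding, and one leaves the arm effect essentially unchanged. None tells the reader how delay bears on the randomised comparison.

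Under coding B the SE increase is 15% to 100% for assumed r of 1 to 3, with all 190 intervention participants having a wait. The shift in the estimate ran from nil to about 1.4 points in the illustrative settings, and its direction depends on the assumed signs.

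It would be wrong to conclude that the trial's main result is at risk. The intention-to-treat model of section 7.3 does not contain this variable and keeps its planned power. This should be corrected before analysis, but it is not critical.

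**What to change.** - Delete time to clinic as a covariate in the two-arm model of section 7.4.1, and drop Table 15 in its present form.
- Replace it with a regression, within the intervention arm only, of each BPI score on the participant's own waiting time, adjusted for centre and baseline BPI. State that non-attenders have no wait and are excluded, and label the result non-randomised and exploratory.
- In the new table footnote, name the baseline covariate actually used. The present footnote gives baseline OKS where section 7.3 gives baseline BPI, which is a separate inconsistency.
- Do not substitute an interaction between arm and the median wait by centre and calendar quarter. Those medians would come from waits observed after randomisation in one arm, so they are not defined at randomisation. They would also be thin: 4 centres × 10 quarters = 40 cells for about 380 × 2/3 = 253 intervention participants, or about 6 per cell if spread evenly.
- Review section 7.6.3 together with this. It restricts the primary analysis to patients whose clinic fell within three months of surgery, a condition controls cannot meet, and does not say how controls are handled.

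The cost is SAP wording, one table, a few lines of code and an entry in Table 51. The downside is that the between-arm version of Table 15 is lost.

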7.4.2 Secondary outcomes

The secondary outcomes will be analysed using appropriate regression models in a similar manner to the primary analysis. The models will adjust for trial centre, baseline BPI pain score and also the baseline scores of the outcome for which it is modelling. A summary of the primary and secondary outcomes can be seen in **Table 13.** Further adjustment for any observed baseline imbalance will only be made for secondary outcomes in the unlikely event that such adjustment had a material effect on the results for the primary outcomes, or if there is a particular cause for concern as a consequence of a known strong relationship between a specific outcome and an individual variable demonstrating (chance) imbalance at baseline.

Results from the secondary analysis will be presented in Table 16.

7.5. Model assumptions and Model Fit

For the above analyses, the following assumptions must be satisfied for the regression models to provide trustworthy results.

Assumptions for Linear regression:

- 1. Continuous outcome variable.
- 2. One or more explanatory variables can be categorical or continuous.
- 3. Linear relationship between each explanatory variable vs. Pain score to be checked using a scatter plot of the outcome variable and each explanatory variable in turn.
- 4. Homoscedasticity to be checked using plots of residuals.
- 5. Normally distributed outcome variable to be checked with a histogram and a Q-Q plot. If data are not normally distributed, we will consider the appropriateness of using a suitable transformation such as a log transform, bearing in mind the robustness of the standard regression model.
- 6. No or little multicollinearity we will verify the associations between explanatory variables using contingency tables and correlation coefficients as appropriate.

We will also check for multi-collinearity in our logistic regression models in the same manner.

Assumptions for Logistic regression:

- 1. Dichotomous outcome variable (eg, CWP(M) status: Y/N).
- 2. One or more explanatory variable.
- 3. Independent observations (the same patient cannot be recruited twice).
- Linear relationship between the continuous explanatory variables and the logistic transformation of the outcome variables – to be checked using a scatter plot of the outcome variable and each explanatory variable in turn.

Model fit for linear regression models will be assessed by comparing the observed values to the fitted values produced by the model. These will be presented on a plot of observed values against fitted values. If the model does not fit well, log transformations will be tested to see if this makes a difference to the quality of model fit.

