3.6. Randomisation procedures

After patients have provided written, informed consent to participate and have completed and returned a baseline questionnaire, they will be randomly allocated to the STAR pathway or usual care. Randomisation will occur as soon as possible after the baseline questionnaire is received by the research team. Randomisation with allocation concealment will be conducted remotely via the Bristol Randomised Trials Collaboration using a web-based randomisation system. Randomisation will take place on a 2:1 basis to ensure that the intervention service is running at sufficient capacity to enable a pragmatic assessment of its effectiveness and, particularly, cost-effectiveness. If the intervention is operating to a sufficient degree of capacity per-protocol and CACE analyses will be more reliable and have higher power. To ensure reasonable balance between the two treatment groups, allocation will be minimised by pain in the replaced knee (assessed with both the Brief Pain Inventory Severity and the Brief Pain Inventory Interference Scales – these scores are both categorised using tertiles of STAR PACE data for these scores) and stratified by orthopaedic centre. Randomisation will be performed by a member of the research team at the co-ordinating centre and the local researcher at each site will then inform participants of the result.

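### With 2:1 allocation, no action is attached to a failed equal-variance check for the co-primary models; robust standard errors would settle this cheaply

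*SAP*

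**What the plan says.** Section 3.6 fixes the allocation: "Randomisation will take place on a 2:1 basis". Section 7.3 says that the two BPI scales "will be analysed to compare treatment groups using linear regression", adjusted for centre as a fixed effect and for baseline BPI. No robust, Welch or bootstrap variance is named there or elsewhere.

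Section 7.5 introduces a list of assumptions on which the trustworthiness of the results is said to depend. Item 4 reads "Homoscedasticity to be checked using plots of residuals". No criterion for failure and no consequence follow.

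Item 5, a separate item on normality, offers a transformation (a log transform is the example), "bearing in mind the robustness of the standard regression model". The end of the section allows log transformations again if the fit is poor. Neither is tied to item 4.

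The sensitivity analyses in 7.6 deal with missing data, overlap with other trials, per protocol and CACE estimates, clinic timing and repeated measures. None deals with unequal variance.

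**The concern.** Ordinary linear regression pools the residual variance over the two arms. With equal arms this does little harm when their spreads differ. With 2:1 allocation the pooled figure is dominated by the larger arm, while the true variance of the difference is driven more by the smaller arm. The standard error is then too small if usual care is the more variable arm and too large if the intervention arm is. A larger sample does not cure this, because the bias depends on the allocation ratio and the SD ratio and not on the total.

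At stake are the confidence intervals and p-values of both co-primary comparisons and of the linear secondary models. The plan calls the assumption necessary but leaves the response to its failure to be chosen once the data have been seen.

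Some difference in spread is conceivable. The pathway leads to differing numbers of referrals (Figure 3), which could widen the intervention arm. The BPI scales are bounded at 0 (Table 13), which could compress whichever arm scores lower. These two mechanisms may act in opposite directions.

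**Working it through.** **Inputs from SAP 3.7.** 380 randomised, 25% loss, so 380 × 0.75 = 285 analysed; at 2:1 this is nI = 190 and nC = 95. The test is carried out "using a 2-sided 5% significance level". The SD "for patients with long-term postsurgical pain has been observed to be approximately 2", with no figure by arm. The target is "a difference between intervention and control groups of between 0.7 and 0.8 scale points for both scales".

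**The plan's own power figure.** In SD units the standard error is √(1/190 + 1/95) = 0.1257.
- 0.35 SD: Φ(0.35/0.1257 − 1.96) = Φ(0.825) = 79.5%
- 0.40 SD: Φ(0.40/0.1257 − 1.96) = Φ(1.223) = 88.9%

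The stated 80% to 90% is reproduced to within about one point. This calculation uses one common SD.

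**Effect of unequal SDs.** Apart from degrees of freedom:
- variance reported by the model: sI²/nC + sC²/nI
- true variance: sI²/nI + sC²/nC

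Each arm's variance is divided by the other arm's size. The two expressions agree if nI = nC or sI = sC. Let k = √(model variance / true variance). The actual two-sided type I error is then 2Φ(−1.96k).

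With sI = 1 and sC set to the assumed control/intervention ratio:

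| Ratio | Model variance | True variance | k | Type I error |
|---|---|---|---|---|
| 1.25 | 0.01875 | 0.02171 | 0.929 | 6.9% |
| 1.10 | 0.01690 | 0.01800 | 0.969 | 5.8% |
| 1.00 | 0.01579 | 0.01579 | 1.000 | 5.0% |
| 0.90 | 0.01479 | 0.01379 | 1.036 | 4.2% |
| 0.80 | 0.01390 | 0.01200 | 1.076 | 3.5% |

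**Power with sI = 2.5 and sC = 2.0 (assumed).**
- Model variance: 6.25/95 + 4/190 = 0.0868, SE 0.2947
- True variance: 6.25/190 + 4/95 = 0.0750, SE 0.2739
- k = 1.076, so the effective critical value is 1.96 × 1.076 = 2.109
- 0.8 points, ordinary SE: Φ(0.8/0.2739 − 2.109) = Φ(0.812) = 79%
- 0.8 points, correct SE: Φ(0.8/0.2739 − 1.96) = Φ(0.961) = 83%
- 0.7 points, the lower end of the target: 67% against 72%

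**Check by simulation.** Regression with one baseline score and four centres, 10,000 trials per setting, no mean difference:

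| Intervention/control SD ratio | Ordinary SE | HC3 |
|---|---|---|
| 0.80 | 6.8% | 4.9% |
| 1.00 | 5.1% | 5.0% |
| 1.25 | 3.7% | 5.0% |

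A smaller simulation (4,000 trials per setting, two baseline scores) gave HC3 4.5% against 4.9% for the ordinary SE at equal SDs. Its Monte Carlo error is about √(0.05 × 0.95/4000) = 0.3 percentage points.

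**The case against.** Several stronger readings are tempting, and the document does not support them.

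- **That the SAP claims regression is robust to unequal variance.** It does not. The remark on robustness belongs to the normality item. The lead-in to the list treats equal variance as a requirement.
- **That a log transform is the only remedy for any failed check.** It is an example, and it is tied to non-normality or poor fit. Section 7.3 also says that the checks serve to confirm that the method is the right one, so a failed check is meant to bear on the choice of method. What remains is narrower: for item 4 neither a threshold nor an alternative is stated.
- **That the SAP specifies a common-variance standard error.** It names none. The ordinary one is implied by unqualified linear regression.
- **That the trial's intervals will be wrong.** Nothing in the SAP shows that the arm SDs differ.

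The size can also be contested. If the pathway affects no patient, the arms share one distribution and the ordinary standard error is valid. A type I error of 6.9% needs an intervention that cuts residual variance by 36% (1 − 1/1.25²) while leaving the mean exactly unchanged. In the other direction, SDs of 2.5 and 2.0 imply individual effects with SD √(2.5² − 2.0²) = 1.5 if these are independent of the untreated score. That is about twice the target difference.

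Finally, linear regression with residual diagnostics is a legitimate pre-specified analysis. These objections stand. They limit the weight of the point, but they do not supply the missing action for item 4.

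**Conclusion.** The point holds as a cheap improvement and not as an error in the plan. Under 2:1 allocation the implied standard error is biased if residual SDs differ between arms. The SAP calls equal variance necessary but pre-specifies neither an action on failure nor a sensitivity analysis.

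The consequence is conditional and modest: under one percentage point of type I error for an SD difference of about 10%, about 1.5 to 2 points for 20 to 25%, and about four points of power for a 0.8-point difference in the 2.5/2.0 example. These figures rest on 190 and 95 analysed and on assumed SD ratios. At a ratio of 1 there is no error, and the treatment estimate is unaffected at any ratio. The algebra is certain; whether this trial would be affected cannot be told from the SAP.

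**What to change.** In 7.3 and 7.4.2, and in those sensitivity repeats that are linear regressions, state that standard errors will be heteroscedasticity-consistent by default, for example HC3 (in Stata, `regress` with `vce(hc3)`). Keep the residual plots in 7.5 as description, so that no choice of standard error depends on them.

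The cost is one sentence in the SAP and one option in the code. The estimate and the estimand stay the same. A log transform, by contrast, would change the estimand and is undefined at a BPI score of 0 without an offset. The downside is at most slight conservatism when variances are equal: simulated type I error with HC3 was about 4.5% to 5.0%.

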9.3. Outcome summaries

Table 13: Primary and Secondary endpoint summary

Outcome measure	Type of data	Range of values	Regression model	Efficacy parameters
BPI – Pain severity scale	Continuous	0-10 (best to worst)	Linear regression	Mean/Median/Log mean score
BPI – Pain Interference scale	Continuous	0-10 (best to worst)	Linear regression	Mean/Median/Log mean score
Oxford Knee Score (OKS)	Continuous	0-48 (worst to best)	Linear regression	Mean/Median/Log mean score
Douleur Neuropathique 4 (DN-4)	Continuous	0-7 (best to worst)	Linear regression	Mean/Median/Log mean score
PainDETECT	Continuous	-1-38 (best to worst)	Linear regression	Mean/Median/Log mean score
Hospital Anxiety and Depression	Ordinal	Each subscale:	Linear regression with dummy	Mean/Median/Log mean score
Scale (HADS)		0-21 (best to worst)	variables	
		normal score (0-7); borderline anxiety/depression (8-10)		
		and clinical anxiety/depression (≥11)		
Pain Catastrophizing Scale	Continuous	The Rumination Scale: 0-16 (best to worst)	Linear regression	Mean/Median/Log mean score
		The Magnification Scale: 0-12 (best to worst)		
		The Helplessness Scale: 0-24 (best to worst)		
		Whole score: 0-52 (best to worst)		
Pain Solution Questionnaire (PaSol)	Continuous	Solving Pain: 0-24 (worst to best)	Linear regression	Mean/Median/Log mean score
		Meaningfulness of Life despite Pain: 0-30 (worst to best)		
		Acceptance of Insolubility of Pain: 0-18 (worst to best)		
		Belief in Solution: 0-12 (worst to best)		
Self-Administered Patient	Continuous	25-100	Linear regression	Mean/Median/Log mean score
Satisfaction Scale for Primary Hip and		(worst to best)		
Knee Arthroplasty				
ICECAP-A	Continuous	-0.001 to 1 (worst to best)	Linear regression	Mean/Median/Log mean score
Short Form-12	Continuous		Linear regression	Mean/Median/Log mean score
Body Map	Binary	0/1: CWP(M) or not	Logistic regression	Odds ratio
Q5 Section A	Ordinal	"Rarely", "Sometimes", "Often", "Most of the time", "All	Linear regression with dummy	Mean/Median/Log mean score
		of the time"	variables	
Q8 Section D	Ordinal	"Rarely", "Sometimes", "Often", "Most of the time", "All	Linear regression with dummy	Mean/Median/Log mean score
		of the time"	variables	
Q5 Section L	Ordinal	"Much better", "A bit better", "The same", "A bit	Linear regression with dummy	Mean/Median/Log mean score
		worse", "Much worse"	variables	
Resourse use		Used by Health	n Economics	
EQ-5D-5L		Used by Health	n Economics	

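### Normality is checked on the outcome instead of the residuals, and the analysis scale of the co-primary BPI scores is left open to a log transform chosen after seeing the fit

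*SAP*

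**What the plan says.** Section 7.5 sets out the assumptions for the analyses described before it, which include the co-primary analysis in section 7.3.

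- The normality item reads "Normally distributed outcome variable to be checked with a histogram and a Q-Q plot". If the data fail it, "we will consider the appropriateness of using a suitable transformation such as a log transform, bearing in mind the robustness of the standard regression model".
- Residuals appear in one item only: "Homoscedasticity to be checked using plots of residuals".
- A separate paragraph on model fit, based on plots of observed against fitted values, says "If the model does not fit well, log transformations will be tested to see if this makes a difference to the quality of model fit". The robustness caveat is not repeated there.
- Table 13 (section 9.3) gives both BPI scales a range of 0 to 10, 0 being best, and lists "Mean/Median/Log mean score" as their efficacy parameter.

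The plan is otherwise built on scale points. Section 3.7 sizes the trial for a difference of 0.7 to 0.8 points and notes that "differences of approximately one scale point can be deemed the minimally important difference for both of these scales". The primary results shell, Table 14, has a column for the difference in means with its confidence interval.

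**The concern.** Two things are wrong in what is written.

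First, the check is aimed at the wrong quantity. Linear regression assumes normal errors given the covariates. A BPI score can look skewed overall because of baseline pain, centre or the treatment effect while the residuals are well behaved, and the reverse can also occur. The check can therefore prompt a change of model for no reason, or miss a reason.

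Second, the response is left open for the trial's main result. There is no criterion for poor fit, no statement of which scale would be primary if a log fitted better, and no rule for scores of 0. The logarithm of 0 is undefined, so without an offset those patients become missing. On BPI a score of 0 means no pain, and an effective treatment produces more such patients in its own arm. Even with an offset, the result would no longer be the quantity for which the trial was sized.

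**Working it through.** **1. The plan's own power figure.** Inputs from section 3.7: 380 randomised, 25% loss, 2:1 allocation, two-sided 5%, SD about 2, standardised differences 0.35 to 0.40 (0.7 to 0.8 points), power 80% to 90%.

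- Analysed: 380 × 0.75 = 285, that is 190 and 95.
- Power = Φ(d × √(190 × 95 / 285) − 1.96), with √63.33 = 7.958.
- d = 0.35: 2.785 − 1.96 = 0.825, power 79.5%.
- d = 0.40: 3.183 − 1.96 = 1.223, power 88.9%.

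The stated figures reproduce. They belong to a raw-scale comparison of means and stay as they are if that scale is kept.

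**2. Where a log is undefined.** Ranges from Table 13:

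| Outcome | Range | Value at or below 0 means |
|---|---|---|
| BPI severity, BPI interference (co-primary) | 0 to 10 | best |
| DN-4 | 0 to 7 | best |
| PainDETECT | −1 to 38 | best |
| OKS | 0 to 48 | worst |

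The value −1 arises for PainDETECT alone, a secondary outcome. For OKS a log would lose the worst patients, not the best.

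**3. What losing the zeros could do.** The SAP gives no expected means or share of zeros, so the control means below are assumptions. Simulation: 4,000 trials, 190 and 95 patients, normal scores with SD 2 and a true shift of −0.75, rounded to 0.25, bounded at 0 and 10, compared by t-test.

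| Control mean | Zeros, control / intervention | Mean difference, all / non-zero | Power, raw / log with zeros lost |
|---|---|---|---|
| 5 | 0.7% / 2.0% | −0.74 / −0.70 | 85% / 76% |
| 4 | 2.6% / 5.9% | −0.72 / −0.62 | 84% / 68% |
| 3 | 7.5% / 14.4% | −0.68 / −0.53 | 83% / 58% |
| 2.5 | 11.8% / 20.8% | −0.64 / −0.48 | 83% / 51% |

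With a shift of 0.7 and control mean 4, power is 79% raw, 62% on the log with zeros lost and 75% on log(y + 1). These are unadjusted tests, whereas section 7.3 adjusts for centre and baseline BPI.

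**4. Units.** In these simulations the log analysis gives a ratio of geometric means of about 0.82 to 0.84. Read as a ratio of typical scores, 0.82 corresponds to 5 × 0.18 = 0.90 points at a control level of 5, but 3 × 0.18 = 0.54 points at a level of 3. One log result can thus lie above or below the 0.7 to 0.8 point target depending on the control level.

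**5. Type I error when the scale is chosen from the data.** With no treatment effect, choosing the scale by residual skewness gave 4.5% to 5.4%. Taking the smaller of the raw and log p-values gave 7.1% to 7.5%.

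**The case against.** The best defence is that the SAP does not commit to a log. For non-normality it only considers one and says that the standard model is robust. That is sound: raw-scale regression on a clearly skewed 0 to 10 score kept 95.6% coverage at 190 against 95. The fit paragraph tests logs without saying that they would replace the primary result. Section 7.3, the sample size and Table 14 all point to the raw scale, and the Table 13 entry is repeated for every linear-regression row and reads like a generic menu.

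This limits the point but does not remove it. A generic menu attached to a co-primary outcome still leaves the estimand unfixed, and the fit paragraph is worded more firmly than the normality item.

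A reader might also infer three stronger things that the SAP does not support:

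- *That a failed normality check leads to dropping the best responders.* Transformation is discretionary, and loss of zeros assumes no offset. The SAP is silent on offsets.
- *That the trial stands to lose the power shown above.* Those scores are near-normal, and a log makes them worse. At control mean 4 (shift 0.7), skewness goes from 0.18 to about −1.35, so a test based on fit should reject the log. For skewed scores, where a log might be adopted, one gamma example (mean 3, shift 0.7) gave 77% raw, 65% with zeros dropped and 72% with log(y + 1). Other skewed shapes can favour the log.
- *That the primary p-value is invalid.* Inflation to about 7% needs selection on the p-value, whereas section 7.5 ties the choice to fit.

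**Conclusion.** The point holds in a limited form and should be corrected. The stated normality check is on the wrong quantity, and the scale of the co-primary analysis can be chosen after seeing the data by a transform that is undefined at the best BPI score. Its result could not be compared with the trial's own target, minimally important difference or primary results table.

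No figure in the SAP changes. A specific power loss or bias cannot be claimed: it rests on assumed score distributions, on the share of zeros and on whether an offset would be used, and its direction can vary. The firm consequence is a possible change of estimand. Loss of pain-free patients follows only if a log is adopted without an offset.

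**What to change.** - In section 7.5, check normality on the model residuals, alongside the residual plots already planned.
- State that the co-primary estimate is the adjusted difference in means on the original 0 to 10 scale whatever the diagnostics show. If residuals are clearly non-normal or heteroscedastic, keep the model and use robust or bootstrap standard errors.
- In Table 13, remove the median and log-mean options for the two BPI scales.
- Keep any transformed analysis as a sensitivity analysis, and state how scores at or below 0 are handled, including for DN-4, PainDETECT and OKS if they are transformed.

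The cost is a few lines of SAP wording and an entry in the amendment log (Table 51). Sample size, data collection and the layout of Table 14 are unaffected.
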